3.2 Outcome Measures

3.2.1 Primary Outcome: Hierarchical Composite Outcome

The primary outcome for the PERFORM trial will be a patient-centered hierarchical composite endpoint, including the four constructs we identified in our stakeholder and patient engagement framework: 1) Mortality as assessed at 12 months, 2) Physical function as assessed at 4 months using the Patient-Reported Outcomes Measurement Information System (PROMIS®) Global Physical Function score, and 3) Number of days at home as determined at 12 months. The data (**Table 2**) below has been extrapolated from the literature and will be hierarchically assessed in the order listed below. The hierarchical order was determined by discrete choice experiment responses from surgeons, caregivers and patient partners (n=86) that allowed for prioritization of the outcomes within the hierarchy.

Table 2. Expected Proportion of Outcomes in the Sample (Stratified by Treatment Arm)

Level	Outcome	Expected Outcomes		
		Overall	Internal Fixation	Resection and Reconstruction
1	Mortality at 12 months	30%	30%	30%
2	PROMIS Global Physical Function (patient-reported outcome measure) * at 4 months	3.5	4.0	3.0
3	Days at Home ** at 12 months	320	300	340

* Higher values = better function, minimal clinically important difference is 0.5. 'To what extent are you able to carry out your everyday physical activities such as walking, climbing stairs, carrying groceries or moving a chair?' (Range 5: completely to, 1: not at all).

** Days with no interaction with the healthcare system, patient diary reported

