4.4 Randomization

After providing informed consent, participants will be randomized in a 1:1 ratio to receive either resection and reconstruction or internal fixation. A centralized web-based randomization system (www.randomize.net) will be used to ensure the concealed allocation of participants. Treatment allocation will be determined using random variable block sizes to avoid a substantial imbalance in the number of participants assigned to each treatment group. To ensure balance across groups for any key prognostic and treatment-related variables, such as regional differences in MBD management, the randomization process will be stratified by: 1) impending or pathologic fracture, and 2) clinical site.

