	4 Month	4 Month	Follow-Up Data Package: X-rays; PROMIS® Physical Function questionnaire; Demographics, health-related questions, Mortality Status; Patient-reported days at home; Recurrence of cancer; SAEs
	6 Month	6 Month	Follow-Up Data Package: X-rays; PROMIS® Physical Function questionnaire; Demographics, health-related questions, Mortality Status; Patient-reported days at home; Recurrence of cancer; SAEs PROMIS®-PROPr questionnaire
	9 Month	9 Month	Follow-Up Data Package: X-rays; PROMIS® Physical Function questionnaire; Demographics, health-related questions, Mortality Status; Patient-reported days at home; Recurrence of cancer; SAEs
	12 Month	12 Month	Follow-Up Data Package: X-rays; PROMIS® Physical Function questionnaire; Demographics, health-related questions, Mortality Status; Patient-reported days at home; Recurrence of cancer; SAEs PROMIS®-PROPr questionnaire

PROMIS®: Patient-Reported Outcomes Measurement Information System; PROPr: PROMIS®-Preference Scoring System

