5.0 Statistical Plan

5.1 Sample Size Determination

The use of hierarchically assessed composite outcomes is becoming more frequent in clinical trials, and it offers several benefits. By utilizing a pre-defined rank, statistical power increases while avoiding concerns of increased type I errors due to multiplicity. This ranked approach also aligns with clinical practice as patients and care providers are typically interested in the treatment effect on multiple outcomes with a defined hierarchy. Detailed simulations were performed to determine the appropriate sample size to adequately power the study. **Table 5** lists the distributional assumptions for each component of the composite outcome by treatment arm. Using 10,000 simulations of these distributions, we determined that 300 patients (150 per group) provided over 90% power to detect superiority with a two-sided alpha of 5% tested with the U-statistic described by Bebu and Lachin²⁶. To account for up to 10% attrition, the trial plans to enroll 334 patients.

Table 5 : Input for sample size estimation.

Rank	Outcome	Resection and Reconstruction	Internal Fixation
1	Death within 12 months	30%	30%
2	Physical function (ability to perform everyday activities) by 4 months		
	Unable to do	5%	10%
	With much difficulty	20%	25%
	With some difficulty	40%	40%
	With little difficult	25%	20%
	Without any difficulty	10%	5%
3	Days at home within 365 days, mean (SD)	340 (20)	300 (20)

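### Level 2 of the primary composite is defined, powered and scheduled in ways that do not match, and the stated power holds only if the collected measure ties about as often as a five-category item

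*Protocol*

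**What the plan says.** Level 2 is physical function at 4 months, and it is described in three places.

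- **Definition.** The Study Summary and section 3.2.1 name the PROMIS Global Physical Function score. The footnote to Table 2 shows one question about everyday physical activities, with "Range 5: completely to, 1: not at all", states that higher is better, and gives a minimal clinically important difference (MCID) of 0.5. Table 2 expects 4.0 with internal fixation and 3.0 with resection and reconstruction.
- **Power.** Table 5 in section 5.1 lists "Physical function (ability to perform everyday activities) by 4 months" with five response options graded by difficulty, the best being "Without any difficulty". The percentages from worst to best are 5/20/40/25/10 for resection and 10/25/40/20/5 for fixation. From these inputs the section reports that "300 patients (150 per group) provided over 90% power to detect superiority with a two-sided alpha of 5" per cent, and adds: "To account for up to 10% attrition, the trial plans to enroll 334 patients".
- **Collection.** The Study Flow table in section 4.6 lists a "PROMIS® Physical Function questionnaire" at every follow-up visit. It gives neither item count nor scoring, and no measure called Global is scheduled at any visit.

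Section 5.2.2 sends a pair to the next level only if it is not separated at a higher one. It states no margin for physical function.

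**The concern.** In a hierarchical comparison, how finely level 2 is graded decides how often level 3 is consulted. Table 5 assumes no mortality difference (30% in each arm), a modest shift in physical function, and a 2 SD difference in days at home (340 versus 300, SD 20). Much of the planned effect therefore sits at level 3, and only pairs tied on physical function can reach it. A five-category item ties often; a fine-grained score rarely does.

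If the scheduled questionnaire is not the item that was defined and powered, the stated power may not apply to the endpoint actually analysed. A later analysis plan cannot recover a 4-month item that was never asked. Tables 2 and 5 also disagree on the direction and size of the expected level-2 effect, so they cannot both describe the variable on which the trial is planned.

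**Working it through.** **Inputs.** From section 5.1: 150 per group, two-sided 5%, the Table 5 distributions, 10% attrition. From section 4.4: "participants will be randomized in a 1:1 ratio". From section 5.2.2: mortality compared as time to event, and a pair passes down only if tied. My assumptions: independent components; exponential death times with 30% dead at one year; pairs in which both died, when passed down, given Table 5 values at the lower levels. Local recurrence, which section 5.2.2 adds as a last level, has no input in Table 5 and was left out.

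**Enrolment.** 300 / 0.9 = 333.3, so 334 is reproduced.

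**Expected values.** Table 5 scored 1 to 5:
- Resection: 0.05×1 + 0.20×2 + 0.40×3 + 0.25×4 + 0.10×5 = 3.15.
- Fixation: 0.10×1 + 0.25×2 + 0.40×3 + 0.20×4 + 0.05×5 = 2.85.

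Table 5 thus gives +0.30 for resection, and Table 2 gives −1.0. Swapping the Table 2 columns would correct the sign but not the size. With Table 2 as printed (SD 1 assumed), the simulated win ratio is about 0.71–0.75, against resection.

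**Ties with five categories.** 0.05×0.10 + 0.20×0.25 + 0.40×0.40 + 0.25×0.20 + 0.10×0.05 = 0.27. Resection wins 44.25% of level-2 comparisons and loses 28.75%.

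**Share of all pairs reaching days at home.**
- Time-to-event mortality: only pairs with both alive pass level 1, 0.7² = 0.49. Then 0.49 × 0.27 = 13.2%.
- 12-month status: pairs both alive or both dead pass, 0.49 + 0.09 = 0.58. Then 0.58 × 0.27 = 15.7%.

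Resection wins a comparison on days at home with probability Φ(40 / (20√2)) = 0.92.

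**Latent effect.** Probit differences at the four Table 5 cut-points are 0.36, 0.29, 0.29 and 0.36 SD. The base value for finer scores was 0.31 SD; the continuous case was also run at 0.29 and 0.36.

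**Power by simulation.** The test was the log win ratio with its large-sample U-statistic variance, with 10,000 replicates for the five-category rows and 2,000–2,500 for the others. In each cell the first figure uses 12-month death status and the second the time-to-event rule.

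| Level 2 measure | Pairs reaching days at home | Power |
|---|---|---|
| Five categories (Table 5) | 15.7% / 13.2% | 90.6% / 78.5% |
| About 9 levels, no margin | 7.9% / 6.7% | 70% / 54% |
| About 17 levels, no margin | 4.5% / 3.8% | 54% / 41% |
| Steps of 0.2 SD, no margin | 3.2% / 2.7% | 47% / 35% |
| Continuous, no margin | 0% / 0% | 30–41% / 22–30% |
| Continuous, 0.5 SD tie margin | 15.6% / 13.2% | 92% / 82% |

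The first row reproduces the stated power of over 90% when mortality is 12-month status. A second simulation gave 89% / 79% for five categories, 32% / 24% for the continuous score and 92% / 81% with the margin. The Finkelstein–Schoenfeld form of the test changed power by about one percentage point or less.

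**The case against.** The strongest reply is that this is a labelling problem. Several parts of it stand.

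- The Table 2 footnote item and the Table 5 scale are both five-level items on everyday physical activities. Under Table 5's distribution they give the same tie rate and the same power, so choosing between them costs nothing.
- Nothing says that the scheduled questionnaire has several items. Section 4.6 describes it as short and low in burden, which fits the single item under an abbreviated name.
- A reader might infer that sites will collect different instruments. Sections 6.0, 6.1.1 and 6.2.1 do not support that: sites receive the study CRFs and enter data into one trial database.
- A reader might infer that an MCID of 0.5 is impossible on an integer item. A single pair cannot differ by 0.5, but group means can, and section 5.2.3 analyses patient-reported outcomes by linear regression. The open question is what role the figure has. The Table 5 SD is about 1.0, so 0.5 points is roughly 0.5 SD, but section 5.2.2 does not say that it serves as a pairwise margin.
- A tie margin could reasonably be left to the statistical analysis plan.

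The reply does not remove the mismatch between the defined, powered and scheduled measures, or the conflict between Tables 2 and 5. Instrument, response scale and visit schedule are protocol content.

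**Conclusion.** The inconsistency is real and concerns a component of the primary endpoint. Its effect on power is conditional.

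- With either five-level item and Table 5's distribution, power is about 90% with 12-month status and about 79% with the time-to-event rule. That gap comes from the mortality rule, not from level 2.
- With a finer score and no tie margin, power is about 54–70% at about nine levels and about 22–41% for a near-continuous score, with intermediate scores in between.
- A 0.5 SD margin on a continuous score restores about 81–92%.

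A reader might infer that the trial as written has less than 50% power. The document does not support that: power below 50% under both mortality rules needs a fine-grained score and no margin, and the protocol establishes neither. The finer-score figures rest on an assumed number of score levels, the latent effect implied by Table 5, and independence between components. The conflict between Tables 2 and 5 needs no assumption beyond scoring the Table 5 categories 1 to 5.

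**What to change.** 1. Name one instrument, response scale and scoring for level 2, and use it identically in the Study Summary, section 3.2.1 with Table 2, the Study Flow table, Table 5 and section 5.2.2.
2. Correct the Table 2 expected values so that they agree with Table 5 in direction and size.
3. Confirm that the CRF collects the chosen measure at 4 months.
4. If a multi-item score is chosen, state the pairwise tie margin below which a pair passes to days at home.
5. State whether the MCID of 0.5 refers to group means or is a pairwise margin. It need not be deleted.
6. Re-run the simulation for the chosen measure and tie rule under the mortality comparison of section 5.2.2, and restate the power.

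The cost is protocol wording, a CRF check and one re-run of an existing simulation. The restated power may be less favourable than the present figure. The CRF check should come before 4-month visits accrue, because the missing item could not be collected afterwards.

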3.2.2 Secondary Outcomes

We will also assess each component listed in **Table 2** above as independent endpoints and the composite outcome at three- and six-months post-surgery as secondary outcomes. Another key secondary outcome will be the PROMIS-PROPr (PROMIS-Preference) utility score - encompassing mental and physical health, quality of life at baseline, six months, and 12 months. This secondary outcome aligns with our patient and caregiver qualitative research themes. The PROMIS-PROPr combines scores from seven PROMIS domains into a single preference-based score (also called a health utility score), which captures the preferences of the general adult population. The total number of items that the patient answers are 31. This instrument gives four different scores: health utility score, domain level scores (one for each of the following domains: physical function, anxiety, depression, fatigue, sleep disturbance, social roles and activities, pain interference, cognition, and pain intensity), physical component score, and a mental component score.

4.0 Study Methods and Procedures

4.1 Study Setting

Under the leadership of the Principal Investigator, our trial team within the Department of Surgery Methods Centre at McMaster University will centrally manage the PERFORM trial. For the definitive trial, we intend to recruit patients from approximately 20-30 clinical sites across Canada and the United States, as well as select international sites with whom we have a history of productive collaboration. Clinical sites will be carefully screened prior to receiving an offer to participate in the trial. The clinical site inclusion criteria will be: 1) adequate research personnel and infrastructure to manage the trial; 2) sufficiently high MBD volume to complete enrolment within the trial timeline (defined as greater than or equal to 12 eligible patients per year); 3) commitment from all or most of the site's orthopaedic oncologists to participate in the trial and that they are comfortable with randomizing all eligible patients (i.e. no potential bias); and 4) access to the required equipment for the two

surgical procedures. The exclusion criteria are: 1) lack of interest in the trial; 2) anticipated challenges with complying with the protocol; 3) conflicting studies that would inhibit patient participation; 4) financial or contractual constraints; and 5) exceptionally poor performance in the PARITY and/or SAFETY trial(s), if applicable. We will remain mindful of the geographic location and expected participant demographics of each clinical site to ensure that the trial sample is geographically and demographically diverse, and that it adequately reflects the spectrum of patients with MBD.

4.2 Trial Population

Extensive background work has established a zone of equipoise in which surgeons would consider both surgical approaches (reconstruction or internal fixation) to be equally appropriate. This background work included a survey of the field²³ and three investigator meetings. The zone of equipoise, therefore, provides inclusion and exclusion criteria that are acceptable to the field (**Table 4**). All patients 18 years of age or older who present with MBD of the proximal femur and who require surgery will be screened. Patients with Multiple Myeloma and Lymphoma will also be screened and included, if eligible.

Table 4: Inclusion and exclusion criteria

Inclusion Criteria	Exclusion Criteria
Life expectancy of at least 6 months	Lesions isolated to the femoral neck
Lesions in the proximal femur (femoral neck, intertrochanteric region, subtrochanteric region, and combinations thereof)	Lesion with any femoral head involvement
Low or intermediate risk for perioperative morbidity and/or mortality	High risk for perioperative morbidity and/or mortality
No more than 75% and no less than 25% bone loss	Multidisciplinary decision that resection of the entire lesion would be indicated
Mutual (patient and physician) decision to perform surgical management of an impending or realized pathologic fracture due to MBD of the proximal femur has been made.	

4.3 Recruitment and Informed Consent

Ethics approval will be obtained at the Methods Centre and at each clinical site before recruitment begins. Each participating clinical site's locally responsible investigator will oversee the administration of the trial at the site level. To screen MBD patients for eligibility, the locally responsible investigator, along with designated personnel, will develop a site-specific patient enrolment plan. Typically, this plan will include participation in patient rounds and a review of weekly clinic schedules for patients with MBD of the proximal femur. While the management of MBD patients can vary between sites, patients will typically become eligible and will be screened once the surgical management options have been discussed with the patient. The sequence of care a MBD patient typically undertakes is outlined in **Figure 3** below.

The initial introduction of the trial to patients will take place after the discussion of surgical management options has occurred. At this time, patients will be provided with the participant information sheet and informed consent form. Given the surgical nature of the trial interventions, consent to participate in the trial must occur prior to the start of surgery. Therefore, to facilitate an improved consent process that prevents undue decision-making stress for patients awaiting surgery for their impending or realized pathologic fractures, the consent process will, when possible, take place at a later time either on the local inpatient ward (if the patient was admitted from the outpatient clinic or emergency room) or via telephone/email (if the patient was discharged and is to return to the hospital at a later date for surgery). This decision also follows the principle of obtaining consent and enrolling patients as late as possible prior to the start of the intervention to avoid missing eligible patients, as well as to avoid the inclusion of ineligible patients.

[figure not shown]
Trial personnel at each clinical site will obtain informed consent from patients prior to randomization. Either electronic, written, or verbal consent via telephone may be obtained, as approved by the local ethics committee. If a patient is unable to provide informed consent (e.g., language restriction or due to their disease), informed consent will be obtained from their proxy, if available. If a patient leaves clinic prior to being invited to participate in the trial, the local trial personnel site may obtain verbal consent via telephone or electronic consent via email, as per local ethics committee approval. Upon providing informed consent, participants will be followed in the trial for one year. However, they may withdraw their consent at any time.

[figure not shown]
The process of obtaining and documenting informed consent will be completed in accordance with local Good Clinical Practice recommendations. Consent procedures will comply with the appropriate ethics committee and any applicable regulations. At minimum, the following process will be observed by delegated personnel to obtain informed consent:

- Present trial information in a manner that is understandable to the potential trial patient/proxy;
- Discuss the trial with the potential trial patient/proxy and answer any questions they ask;
- Allow the potential trial patient/proxy an opportunity to discuss participation with others, if desired;
- Confirm that the potential trial patient/proxy understands the risks and benefits of participating in the trial and that their participation is voluntary;
- Complete and obtain the appropriate signatures on the approved Informed Consent Form and collect contact information from the trial patient/proxy; and
- Provide the trial patient/proxy with a copy (paper or electronic) of the signed Informed Consent Form.

Trial personnel at clinical sites will be trained to approach any and all potentially eligible patients (should they agree to be approached). They will receive ongoing training at annual Investigators Meetings and monitoring visits, with guidance from our patient partners and trial team.

Figure 3. Typical Sequence of Care of MBD Patients

4.4 Randomization

After providing informed consent, participants will be randomized in a 1:1 ratio to receive either resection and reconstruction or internal fixation. A centralized web-based randomization system (www.randomize.net) will be used to ensure the concealed allocation of participants. Treatment allocation will be determined using random variable block sizes to avoid a substantial imbalance in the number of participants assigned to each treatment group. To ensure balance across groups for any key prognostic and treatment-related variables, such as regional differences in MBD management, the randomization process will be stratified by: 1) impending or pathologic fracture, and 2) clinical site.

4.5 Study Interventions

4.5.1 Internal Fixation

If the participant is randomized to the Internal Fixation treatment arm, the surgery will involve the stabilization of the remaining bone with either an intramedullary nail, plate or screw fixation. All standard surgical principles of stable internal fixation will be followed. The type of fixation, the surgical approach, and the intra-operative use of cement and other adjuvants for disease control will be at the treating surgeon's discretion. We will, however, record these surgical details on the trial CRFs.

4.5.2 Resection and Reconstruction

If a participant is randomized to the Resection and Reconstruction treatment arm, a proximal femoral resection or hip arthroplasty will be carried out as per standard surgical practice. The type of endoprosthesis used for reconstruction will be at the treating surgeon's discretion. Acetabular reconstruction (if any), the surgical

approach, and the intra-operative use of cement and other adjuvants for disease control will also be at the discretion of the treating surgeon. We will, however, record these surgical details on the trial CRFs.

4.5.3 Standardization of Perioperative Care

The random assignment will only specify the type of surgical procedure. To ensure that differences in pre-, peri- and post-operative regimens across clinical sites do not impact trial outcomes, the following key aspects will be standardized. Pre-operatively, prophylactic antibiotics will be administered within one hour of the start of the procedure, with the specific antibiotic at the discretion of the treating surgeon. Post-operatively, antibiotics will continue for 24 hours with the specific choice of antibiotic and regimen at the discretion of the treating surgeon. Thromboprophylaxis will be prescribed, with the specific agent at the discretion of the treating surgeon. All participants will be mobilized within 24 hours of surgery; weightbearing will be advanced as per the treating surgeon's best judgment. The type of anesthesia will be left at the discretion of the local care team. Due to a lack of evidence favoring a particular approach, we will not standardize the use of post-operative hip precautions, physiotherapy/rehabilitation programs and pain management – rather, they will be left at the discretion of the treating surgeon. We will, however, record details of all these variables on the trial CRFs.

